7.7.3 Determination of additional sample size for stage II in cohort F

With an additional sample size of approximately 30 in stage II, the probability to pass the defined Bayesian decision criterion (in [Section 7.1.2](#)) is 96% when the true underlying ORR is 40%. When true underlying ORR is 20%, the probability to pass the defined Bayesian decision criterion is 24% ([Table 7.7.3: 1](#)).

Table 7.7.3: 1

Probability of satisfying statistical criterion after stage II

True ORR	Probability of satisfying statistical criterion after stage II
0.20	0.24
0.25	0.49
0.30	0.72
0.35	0.88
0.40	0.96
0.45	0.98

8. INFORMED CONSENT, TRIAL RECORDS, DATA PROTECTION, PUBLICATION POLICY, AND ADMINISTRATIVE STRUCTURE

The trial will be carried out in accordance with the Medical Devices Directive (93/42/EEC) and the harmonised standards for Medical Devices (ISO 14155, current version).

The trial will be carried out in compliance with the protocol, the ethical principles laid down in the Declaration of Helsinki, in accordance with the ICH Harmonized Tripartite Guideline for Good Clinical Practice (GCP), relevant BI Standard Operating Procedures (SOPs), the EU regulation 536/2014 the Japanese GCP regulations (Ministry of Health and Welfare Ordinance No. 28, March 27, 1997) and other relevant regulations.

Standard medical care (prophylactic, diagnostic and therapeutic procedures) remains the responsibility of the treating physician of the patient.

The investigator will inform the sponsor immediately of any urgent safety measures taken to protect the trial patients against any immediate hazard, as well as of any serious breaches of the protocol or of ICH GCP.

The Boehringer Ingelheim transparency and publication policy can be found on the following web page: trials.boehringer-ingelheim.com. The rights of the investigator and of the sponsor with regards to publication of the results of this trial are described in the investigator contract. As a rule, no trial results should be published prior to finalization of the Clinical Trial Report. The certificate of insurance cover is made available to the investigator and the patients, and is stored in the ISF.

8.1 TRIAL APPROVAL, PATIENT INFORMATION, INFORMED CONSENT

This trial will be initiated only after all required legal documentation has been reviewed and approved by the respective Institutional Review Board (IRB) / Independent Ethics Committee (IEC) and competent authority (CA) according to national and international regulations. The same applies for the implementation of changes introduced by amendments.

Prior to patient participation in the trial, written informed consent must be obtained from each patient (or the patient's legally accepted representative) according to ICH / GCP and to the regulatory and legal requirements of the participating country. Each signature must be personally dated by each signatory and the informed consent and any additional patient-information form retained by the investigator as part of the trial records. A signed copy of the informed consent and any additional patient information must be given to each patient or the patient's legally accepted representative.”

The investigator must give a full explanation to trial patients based on the patient information form. A language understandable to the patient should be chosen, technical terms and expressions avoided, if possible.

The patient must be given sufficient time to consider participation in the trial. The investigator obtains written consent of the patient's own free will with the informed consent form after confirming that the patient understands the contents. The investigator must sign (or place a seal on) and date the informed consent form. If a trial collaborator has given a supplementary explanation, the trial collaborator also signs (or places a seal on) and dates the informed consent.

Re-consenting may become necessary when new relevant information becomes available and should be conducted according to the sponsor's instructions.

The consent and re-consenting process should be properly documented in the source documentation.

8.2 DATA QUALITY ASSURANCE

A quality assurance audit/inspection of this trial may be conducted by the sponsor, sponsor's designees, or by IRB / IEC or by regulatory authorities. The quality assurance auditor will have access to all medical records, the investigator's trial-related files and correspondence, and the informed consent documentation of this clinical trial.

8.3 RECORDS

CRFs for individual patients will be provided by the sponsor. For drug accountability, refer to [Section 4.1.8](#).

8.3.1 Source documents

In accordance with regulatory requirements the investigator should prepare and maintain adequate and accurate source documents and trial records that include all observations and other data pertinent to the investigation on each trial patient. Source data as well as reported data should follow good documentation practices and be attributable, legible, contemporaneous, original and accurate. Changes to the data should be traceable (audit trail). Data reported on the CRF must be consistent with the source data or the discrepancies must be explained.

The current medical history of the patient may not be sufficient to confirm eligibility for the trial and the investigator may need to request previous medical histories and evidence of any diagnostic tests. In this case the investigator must make three documented attempts to retrieve previous medical records. If this fails a verbal history from the patient, documented in their medical records, would be acceptable.

During the site visit the sponsor's CRA or auditor must be granted access to the original patient file (please see [Section 8.3.2](#)).

The investigator must ensure that all patient identifiers (e.g. patient's name, initials, address, phone number, social security number) have properly been removed or redacted from any copy of the patients' source documents before sending them to the sponsor.

If the patient is not compliant with the protocol, any corrective action e.g. re-training must be documented in the patient file.

For the CRF, data must be derived from source documents, for example:

- Patient identification: gender, year of birth (in accordance with local laws and regulations)
- Patient participation in the trial (substance, trial number, patient number, date patient was informed)
- Dates of patient's visits, including dispensing of trial medication
- Medical history (including trial indication and concomitant diseases, if applicable)
- Medication history
- Adverse events and outcome events (onset date (mandatory), and end date (if available))
- Serious adverse events (onset date (mandatory), and end date (if available))
- Concomitant therapy (start date, changes)
- Originals or copies of laboratory results and other imaging or testing results, with proper documented medical evaluation (in validated electronic format, if available)
- Completion of patient's participation in the trial" (end date; in case of premature discontinuation document the reason for it).
- Prior to allocation of a patient to a treatment into a clinical trial, there must be documented evidence in the source data (e.g. medical records) that the trial participant meets all inclusion criteria and does not meet any exclusion criteria. The absence of records (either medical records, verbal documented feedback of the patient or testing conducted specific for a protocol) to support inclusion/exclusion criteria does not make the patient eligible for the clinical trial.

8.3.2 Direct access to source data and documents

The sponsor will monitor the conduct of the trial by regular on-site monitoring visits and in-house data quality review. The frequency of site monitoring will be determined by assessing all characteristics of the trial, including its nature, objective, methodology and the degree of any deviations of the intervention from normal clinical practice.

The investigator /institution will allow site trial-related monitoring, audits, IRB / IEC review and regulatory inspections. Direct access must be provided to the CRF and all source documents/data, including progress notes, copies of laboratory and medical test results, which must be available at all times for review by the CRA, auditor and regulatory inspector (e.g. FDA). They may review all CRFs and informed consents. The accuracy of the data will be verified by direct comparison with the source documents described in [Section 8.3.1](#). The sponsor will also monitor compliance with the protocol and GCP.

8.3.3 Storage period of records

Trial site(s):

The trial site(s) must retain the source and essential documents (including ISF) according to contract or the local requirements valid at the time of the end of the trial (whatever is longer).

Sponsor:

The sponsor must retain the essential documents according to the sponsor's SOPs.

8.4 EXPEDITED REPORTING OF ADVERSE EVENTS

BI is responsible to fulfil their legal and regulatory reporting obligation in accordance with regulatory requirements.

Exemptions from expedited reporting are described in [Section 5.2.7.2](#), if applicable.

8.5 STATEMENT OF CONFIDENTIALITY AND PATIENT PRIVACY

Individual patient data obtained as a result of this trial is considered confidential and disclosure to third parties is prohibited with the exceptions noted below. Patient privacy will be ensured by using patient identification code numbers.

Data protection and data security measures are implemented for the collection, storage and processing of patient data in accordance with the principles 6 and 12 of the WHO GCP handbook.

Treatment data may be given to the patient's personal physician or to other appropriate medical personnel responsible for the patient's welfare. Data generated as a result of the trial need to be available for inspection on request by the participating physicians, the sponsor's representatives, by the IRB / IEC and the regulatory authorities.

8.5.1 Collection, storage and future use of biological samples and corresponding data

Measures are in place to comply with the applicable rules for the collection, storage and future use of biological samples from clinical trial participants and the corresponding data, in particular

- A Quality Management System has been implemented to ensure the adherence with the Principles of Good Clinical Practice as outlined in 'Note For Guidance On Good Clinical Practice' (CPMP/ICH/13 5/95)
- The BI-internal facilities storing and analyzing biological samples and data from clinical trial participants as well as the laboratories' activities for clinical trials sponsored by Boehringer Ingelheim are regularly audited. The analytical groups and the banking facility are therefore assessed to be qualified for the storage and use of biological samples and data collected in clinical trials.

- Samples and data are used only if an appropriate informed consent is available.

8.6 TRIAL MILESTONES

The **start of the trial** is defined as the date when the first patient in the whole trial signs informed consent.

The **end of the trial** is defined as the date of the last visit of the last patient in the whole trial (“Last Patient Out”), or when all patients have been discontinued from study treatment and followed until the end of REP.

The “**Last Patient Drug Discontinuation**” (LPDD) date is defined as the date on which the last patient at an individual trial site ends trial medication (as scheduled per protocol or prematurely). Individual investigators will be notified of SUSARs occurring with the trial medication until 30 days after LPDD at their site.

Early termination of the trial is defined as the premature termination of the trial due to any reason before the end of the trial as specified in this protocol.

Temporary halt of the trial is defined as any unplanned interruption of the trial by the sponsor with the intention to resume it.

Suspension of the trial is defined as an interruption of the trial based on a Health Authority request.

The IEC / competent authority in each participating EU member state will be notified about the trial milestones according to the respective laws.

A final report of the clinical trial data will be written only after all patients have completed the trial in all countries (EU or non-EU) to incorporate and consider all data in the report. The sponsor will submit to the EU database a summary of the final trial results within one year from the end of a clinical trial as a whole, regardless of the country of the last patient (EU or non-EU).

8.7 ADMINISTRATIVE STRUCTURE OF THE TRIAL

The trial is sponsored by Boehringer Ingelheim (BI).

A Coordinating Investigator is responsible to coordinate investigators at the different sites participating in this trial. Tasks and responsibilities are defined in a contract.

A Study Monitoring Committee (SMC) composed of participating investigators and members of the BI trial team will be established to review individual and aggregated safety and efficacy data at regular intervals to determine the safety profile and risk/benefit ratio and

recommend next dose level/does appropriateness of further enrolment. Details of the SMC responsibilities and procedures are described in the SMC charter.

Relevant documentation on the participating (Principal) Investigators (e.g. their curricula vitae) will be filed in the (Investigator Site File) ISF. The investigators will have access to the BI clinical trial portal (Clinergize) to facilitate document exchange and maintain electronic ISF.

BI has appointed a Trial Clinical Monitor, responsible for coordinating all required activities, in order to

- manage the trial in accordance with applicable regulations and internal SOPs,
- direct the clinical trial team in the preparation, conduct, and reporting of the trial,
- ensure appropriate training and information of Local Clinical Monitors (CML), Clinical Research Associates (CRAs), and investigators of participating countries.

The organisation of the trial in the participating countries will be performed by the respective local or regional BI-organisation (Operating Unit, OPU) in accordance with applicable regulations and BI SOPs, or by a Contract Research Organisation (CRO) with which the responsibilities and tasks will have been agreed and a written contract filed before initiation of the clinical trial.

Data Management and Statistical Evaluation will be done by BI according to BI SOPs.

Tasks and functions assigned in order to organise, manage, and evaluate the trial are defined according to BI SOPs. A list of responsible persons and relevant local information can be found in the ISF.

A central laboratory service and an IRT vendor will be used in this trial. Details will be provided in the IRT Manual and Central Laboratory Manual, available in the ISF.

10. APPENDICES

10.1 INSTRUCTIONS FOR USE

Instructions for Pharmacist: available in the ISF.

10.2 BLOOD PRESSURE MEASUREMENT PROCEDURE

Blood pressure measurements should be performed on the same arm and, if possible, by the same person. The machines or devices to be used for blood pressure measurement should be certified. The same method and device must be used throughout the trial for a patient i.e. if a patient receives the first blood pressure measurement for example with an electronic device, the same method and device should be used throughout the study for this patient (without switching to manual blood pressure measurement). On the other hand, inter-patient variability is acceptable, i.e. a study site is allowed to consistently use an electronic device to measure the blood pressure in a given patient throughout the study and a manual technique in another patient. The blood pressure measurement should be taken after the patient has rested quietly in a seated position for at least five minutes.

In Part 1, three blood pressure measurements will be taken two minutes apart and all three results have to be entered in the eCRF.

In Part 2, only a single blood pressure measurement is required per scheduled time point, i.e. one measurement before the study drugs have been administered, and one measurement after the study drugs are administered. Please see [Section 5.2.2](#) for further details, and [Appendix 10.2.1](#) for management guidelines.

10.2.1 Blood Pressure Management and Study Drug Administration Guidelines

Table 10.2.1: 1 BP management and study drug administration guidelines following completion of cycle 1, based on pre-infusion SBP and DBP measured on study drug administration visits.

Pre-infusion clinic BP (mmHg) on pre-planned infusion visits	SBP <160 and DBP <100	SBP 160-179 or DBP 100-109	SBP ≥180 or DBP ≥110	Hypertensive crisis**
Action to be taken with BI 836880 and ezabenlimab	Proceed with study drug administration as scheduled / re-start.	Temporarily delay administration of both study drugs until BP < 160/100.	Delay administration of both study drugs until next pre-scheduled study drug administration.	Discontinue both study drugs.
Antihypertensive treatment	As deemed necessary by the investigator.*	
Wait 10-15 minutes and ensure patient is relaxed, and re-measure BP:
 
 - If BP <160/100 on re-assessment, administer both study drugs; - If SBP remains 160-179 or DBP 100-109, initiate / modify antihypertensive regimens, delay administration of both study drugs, and re-assess within 12-48 hours of antihypertensive agent initiation/modification. 
After 12-48 hours:
 
 - If BP <160/100, administer both study drugs. - If BP remains ≥160/100, repeat after 10-15 minutes; if BP remains ≥160/100 hold study drug administration until next pre-planned infusion visit, and initiate / modify antihypertensive regimens. 	Initiate / modify antihypertensive regimens, and re-assess at the next scheduled infusion visit.	Emergency admission for in-patient care

* Investigators should consider initiating / modifying antihypertensive regimens if SBP < 160 mmHg or DBP > 100 mmHg if their medical assessment is that lowering BP further is clinically indicated (for example, patient has cardiovascular risk factors), and discontinuing or modifying antihypertensive agents if there are symptoms /signs of hypotension.

** Hypertensive crisis defined as patients with significantly elevated blood pressure with signs or symptoms of acute, ongoing target-organ damage.

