- 9, 10 and 11: see [Appendix 10.5 Table 10.5.1: 1](#)
- 

Proprietary confidential information © 2023 Boehringer Ingelheim International GmbH or one or more of its affiliated companies

FLOW CHART (PART 2)

Trial Periods	Screen	Treatment cycles				EOT	Safety Follow-up	FU / EoFU
Cycle		1				2 - 53		
Week		w1 w2 w3				w1		
Visit	Screen	V1 V2 V3				V1		
Day; visit window [days]	-21 to -1	d1	d2	d8; (-1/+2d)	d15; (-1/+2d)	d1; (+2d) for cycle 2; ongoing cycles (-1/+2d)	EoT (when defined)	Last admin +42d;(+3d) every 6 weeks (+/- 3d) until PD
Informed consent / IRT call	X							
Demographics	X							
Medical history	X							
Review of in-/ exclusion criteria	X							
Height	X							
Weight	X	X				X	X	X
ECOG / Karnofsky performance status [@]	X	X				X	X	X
Body temperature	X	X		X		X	X	
Blood pressure, heart rate ¹	X	X	X	X	X	X	X	X
12-lead ECG ²	X	X				X (2,3,4,6, 8, 10,12..)*	X	
Echocardiography ³	X	if clinically indicated				X		
Infectious Screen [§]	X							
General safety laboratory parameters ⁴	X	X		X	X	X	X	
Pregnancy test [§]	X	X				X	X	
Concomitant therapy	X	X	X	X	X	X	X	X
Physical examination ⁵	X	X	X	X	X	X	X	X
Adverse events ⁶	X	X	X	X	X	X	X	X
Eligibility for treatment / IRT call ⁷		X				X		
Admin of ezabenlimab/ BI 836880		X				X		
Disease / response assessment (clinical/imaging) ⁸	X					X		

Clinical Trial Protocol

Proprietary confidential information © 2023 Boehringer Ingelheim International GmbH or one or more of its affiliated companies

Trial Periods	Screen	Treatment cycles				EOT	Safety Follow-up	FU / EoFU
Cycle		1				2 - 53		
Week		w1				w1		
Visit	Screen	V1				V1		
Day; visit window [days]	-21 to -1	d1	d2	d8; (-1/+2d)	d15; (-1/+2d)	d1; (+2d) for cycle 2; ongoing cycles (1/+2d)	EoT (when defined)	Last admin +42d; (+3d) every 6 weeks (+/- 3d) until PD
Pharmacokinetics ⁹		X	X	X	X			

* number in brackets indicate the cycle this visit/assessment is applicable

EoC = End of Cycle; FU1 = 1st Follow-up visit

1 See [Appendix 10.2](#) for BP and HR should be measured before and after study drugs have been administered. Please follow the BP monitoring and study drug administration guidelines in [Appendix 10.2.1](#).

2 ECG for all patients according to [flowchart](#) schedule.- Cycle 1 to 4 pre and post treatment (within 60 min after completion of administration of BI 836880) and thereafter ECG at pre- and post treatment of BI 836880 performed every second cycle (cycle 6,8, 10...etc

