6.2.2 Treatment period(s)

A treatment cycle is defined as 3 weeks of duration. If initiation of a subsequent cycle is delayed due to medical reasons, additional visits beyond Day 21 may be necessary and may be performed at investigator's discretion, and should be recorded in the eCRF.

During cycle 1 (for Part 1 and 2) and 4 (only for Part 1), intensive PK-sampling will be conducted and patients have to be observed closely for any adverse events. Therefore, patients have to come to the clinic during the first four cycles every week to the clinic. In Part 1 additional visits are needed at day 2 for cycles 1, 2 and 4 and at day 3 for cycle 1. In cycles 5 and 6 the patient is requested to come to the clinic on day 8 after administration of study drug. From cycle 7 onwards no additional visits, beside day 1 including drug administration, are requested by protocol. In Part 2 from cycle 2 onwards, no additional visits, beside day 1 including drug administration, are requested by protocol.

For Part 1 and Part 2 disease response assessment by CT/MRI will be performed according to institutional practices and SOC.

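### Blood pressure table: after antihypertensives are first started or changed, the severe non-crisis band (SBP ≥180 or DBP ≥110) gets a later stated re-check than the milder band

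*Protocol*

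**What the plan says.** Table 10.2.1: 1 in Appendix 10.2.1 has a dosing row and an antihypertensive-treatment row, with columns by pre-infusion blood pressure. It applies once cycle 1 is complete. Section 4.1.4 sends sites to it as re-administration criterion 1 in Part 2.

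- **SBP 160-179 or DBP 100-109.** Blood pressure is repeated after 10-15 minutes. If it is still raised, antihypertensives are started or changed, both study drugs are delayed, and the site must "re-assess within 12-48 hours of antihypertensive agent initiation/modification". If it is still at or above 160/100 at that check and on a repeat shortly afterwards, the site is to "hold study drug administration until next pre-planned infusion visit, and initiate / modify antihypertensive regimens".
- **SBP ≥180 or DBP ≥110, no crisis.** Dosing: "Delay administration of both study drugs until next pre-scheduled study drug administration". Antihypertensives: "Initiate / modify antihypertensive regimens, and re-assess at the next scheduled infusion visit".
- **Hypertensive crisis.** This column is defined by signs or symptoms of acute target-organ damage, not by a pressure threshold. A patient above 180/110 without such signs stays in the column before it.

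Section 6.2.2 fixes the spacing of infusion visits: "A treatment cycle is defined as 3 weeks of duration". It adds: "In Part 2 from cycle 2 onwards, no additional visits, beside day 1 including drug administration, are requested by protocol".

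**The concern.** The two non-crisis bands call for the same drug step, starting or changing antihypertensives. The re-check after that step is set in hours for the milder reading and left to the next infusion visit for the worse one. The table's title covers blood pressure management as well as dosing, and Section 6.1, which warns of severe hypertensive episodes, refers sites to this appendix. A site that follows the table literally would look again later at the patient in more danger.

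Hypertension is the leading Grade 3 event of the combination (Section 1.2.1). The protocol also defines persistent hypertension as an adverse event of special interest (Section 5.2.7.1): readings of at least 140 systolic or 90 diastolic lasting more than 2 days despite new or intensified antihypertensive treatment. In the severe band, the table schedules no reading from which this could be established for about three weeks.

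What is at stake is patient monitoring. No endpoint or analysis depends on it.

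**Working it through.** The plan gives no figure to reproduce here. The check compares the latest permitted first blood pressure re-check after the first antihypertensive change in each band.

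**Inputs**

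- Milder band: 12-48 hours (Table 10.2.1: 1).
- Severe band: next scheduled infusion visit (Table 10.2.1: 1).
- Cycle length: 3 weeks (Section 6.2.2).
- Visit window: "d1; (+2d) for cycle 2; ongoing cycles (-1/+2d" days (Flow Chart, Part 2). The table applies after cycle 1, so the next visit is cycle 3 or later and the -1/+2 window applies.
- Weekly visits when dosing is delayed because of an adverse event (Section 5.2.3).

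The 10-15 minute repeat in the milder band comes before any drug change, so it is left out.

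**Latest re-check**

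- Milder band: 48 h = 2 days (earliest 12 h = 0.5 day).
- Severe band, table alone: 3 × 7 = 21 days. With the window, 21 - 1 = 20 to 21 + 2 = 23 days, taking the present visit as on its planned day.
- Severe band, weekly rule applied: 7 days.

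**Comparison with the milder band**

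| Reading of the protocol | Severe band | Ratio to 2 days | Difference |
|---|---|---|---|
| Table alone | 21 days (20-23) | 21/2 = 10.5 (20/2 = 10 to 23/2 = 11.5) | 19 days (18-21) |
| Weekly rule applied | 7 days | 7/2 = 3.5 | 5 days |

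**Limit of the inversion.** In the milder band's last branch, after a second change, the next check is also the next infusion visit: 21 - 2 = 19 to 21 - 0.5 = 20.5 days later. Nothing is inverted there.

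**Do other rules set an early reading for the severe band?**

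- Section 4.1.4 provides for re-evaluation when criteria 2, 3 or 4 fail. Blood pressure is criterion 1, which refers only to this table. Criterion 4 (tolerability) can be reached if the reading is handled as an adverse event.
- Section 5.2.7.2 makes a vital-sign change an adverse event if the investigator judges it clinically relevant. That can bring in the weekly visits of Section 5.2.3, whose stated content is laboratory safety and adverse events, without naming blood pressure.
- Section 5.2.2 ties vital-sign recording to Flow Chart visits.
- Sections 5.2.3, 6.1 and 6.2.2 allow extra visits by discretion. Section 6.2.2, for instance, says that after a medically delayed cycle "additional visits beyond Day 21 may be necessary and may be performed".

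None of these fixes a blood pressure check within days, and the table cell refers to none of them.

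**Numbers exposed.** The protocol gives no count for the ≥180/110 band. For context only, Grade 3 hypertension was reported in 8.4% of 359 patients pooled across the combination trials: 0.084 × 359 = 30.2, about 30. In January 2022, 44 patients of this trial were still on treatment (Section 1.1).

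**The case against.** The strongest reply is that the two checks do different jobs. In the milder band this cycle's dose is still open, and the 12-48 hour reading decides whether it is given. In the severe band the dose has already been forgone, so no dosing decision is pending. On that reading the table follows one rule: check soon while the dose is open, otherwise treat and re-assess at the next infusion visit. The milder band's last branch fits this. It is a fair account of how the layout arose. It does not justify the result, because the instruction sits in the antihypertensive-treatment row and sets when to look again after a drug change, a need that does not end when the dose is forgone.

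Second, other rules should produce earlier readings. A pressure that cancels both drugs would ordinarily be recorded as an adverse event, and a weekly visit to assess raised blood pressure would in practice include measuring it. The persistent-hypertension definition implies follow-up on a scale of about 2 days, and Section 8 leaves standard care with the treating physician. Much of this stands: 7 days is the more realistic outer limit for a careful site, and the table forbids no earlier check. But the special-interest definition and the standard-care clause schedule no reading, and the weekly rule still allows day 7 against day 2.

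Third, the Section 6.1 warning concerns surveillance after an infusion, and these patients are not infused. That is correct. The warning shows only that severe episodes are expected and that sites are sent to this table.

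Fourth, the group is small and uncounted, and recruitment has closed. This limits the weight of the point without removing it.

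**Conclusion.** The concern holds. After the first antihypertensive change, the latest stated re-check is 2 days at 160-179/100-109. At ≥180/110 without crisis it is 21 days on the table alone (20-23 with the window), or 7 days if the event is recorded as an adverse event delaying dosing, the weekly rule is applied and blood pressure is measured at that visit. The severe band is therefore checked 10.5 times later (10-11.5) or 3.5 times later.

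This rests on 3-week cycles, on Part 2 from cycle 2 onwards with no scheduled visit between infusions, and on the crisis column excluding patients without target-organ damage. It applies only to the first antihypertensive change. The number of patients affected cannot be derived from the protocol. The matter should be corrected for patient safety; it does not affect the response-rate endpoint, the sample size or any analysis.

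**What to change.** In the SBP ≥180 or DBP ≥110 cell of the antihypertensive-treatment row, replace the single re-check by two requirements:

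1. Re-assess blood pressure within 12-48 hours of starting or changing antihypertensives, as in the milder band.
2. Measure blood pressure at least weekly until the next infusion visit, with a reference to Section 5.2.3.

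Keep the dose hold in this column as it is.

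Two clerical corrections can go in the same edit and carry no weight in the conclusion. The table's first footnote should read DBP < 100, to match its own column. Section 5.2.2 should point to Appendix 10.2.1; Appendix 10.3 lists immune-related events.

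The cost is one edited cell, two clerical changes and a few extra blood pressure checks in a small, unquantified share of patients. Dosing rules, endpoints and analyses do not change.
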